Interestingly the robotic training appeared to facilitate the effects of conventional therapy. There were significant gains in the Box and Blocks after conventional therapy only if it was preceded by a period of robotic training ( $p = 0.044$ ). Clinically significant gains were present in the Fugl-Meyer when robot therapy was given first and followed by conventional therapy. The mean gain was  $7 \pm 2.2$  points, which was statistically significant ( $p = 0.034$ ). This gain was larger than 10% of full scale (6.6 points), which is considered the minimally clinically important difference (MCID) on this scale (Gladstone 2002, Lo 2010, Page 2012). In the ARAT, the gains at the end of treatment (robot + conventional) did not reach the MCID threshold of 10% or 5.7

points (van der Lee 1999, van der Lee 2001). However, gains following the first period of robot treatment did approach the MCID threshold (gain=5.6±2.1; p=.057).

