### Data analysis

Prior to conducting the main analyses, summary statistics, histograms, and scatter plots will be inspected to verify that distribution assumptions are met. Adjustments (e.g., transformations) to the main dependent measures will be made as necessary to address any problems (e.g., skewness, outliers) that these preliminary analyses uncover. To test Hypotheses, a series of mixed model ANOVAs will be tested, one for each dependent variable, with the within-subject variable being timepoint (pre, after 12 hours of treatment, after 24 hours of treatment, 6 month followup) and the between-subject variable of group (experimental vs. control). A significant effect of timepoint or a significant timepoint x group interaction would be followed with a series of paired t-tests, with Bonferoni corrections. Hypothesis I will be tested with a paired t-test between the pre and post-robotic timepoint (after 12 hours of robotic treatment). Hypothesis II will be tested with a paired t-test between the pre and post-treatment timepoint in the experimental group (after 12 hours of robot and 12 hours of conventional therapy). Additionally a z-test will be performed for the hypothesis that the proportion of subjects with 10% or greater gain at the post-treatment timepoint is significantly greater than zero. A final paired t-test and z-test between pre and 6-month followup timepoints will be performed. If a change is statistically significant, mean changes will be compared to predetermined MCID values of 10% of full scale. To test Hypothesis III, the timepoint x group interaction effect will be examined in the mixed model ANOVA. If significant, gains in the dependent variables will be calculated at the post-treatment and 6-month timepoints (relative to the pre timepoint), and between-group differences will be tested with unpaired t-tests, with Bonferoni corrections.

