### Power Analysis

The power analysis was based on data from our previous pilot study (Brokaw 2014). To address Hypothesis I, we calculated power to detect significant gains after only the robotic training. Using the pre-post changes after the initial period of robotic therapy from our pilot study, the effect size for the ARAT was  $d_z=1.2$ , with pre-post correlation  $r=0.94$ . In order to detect an effect this large, when using a 1-tailed paired t-test with  $\alpha=.05$ , a sample size of **N=8** is required for power > 0.90 (Faul 2009). For the Fugl-Meyer, the effect size was  $d_z=0.74$ , with pre-post correlation  $r=0.85$ , which would require a sample size of **N=18** for power > 0.90.

To power Hypothesis II, the pre-post effect size for gains on the ARAT after the experimental treatment (12 hours of robot + 12 hours of conventional therapy) was  $d_z=0.77$ , with pre-post correlation  $r=0.95$  (only using data from subjects who received robotic therapy followed by conventional therapy). In order to detect an effect this large, when using a 1-tailed paired t-test with  $\alpha=.05$ , a sample size of **N=16** is required for power > 0.90. For the Fugl-Meyer, the pre-post effect size was  $d_z=1.41$ , with pre-post correlation  $r=0.91$ . In order to detect this difference, only **N=6** subjects are required for power > 0.90.

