To address Hypothesis III, we calculated the power to detect the expected differences in gains between the experimental and control groups. The experimental treatment in our pilot study produced gains of 7 (sd=4.9) in the Fugl-Meyer. A recent study reported gains of 2.47 (sd=1.67) on the Fugl-Meyer after 24 hours of conventional therapy in 35 stroke subjects with similar intake Fugl-Meyer scores as in our pilot study (FM = 22.4 vs. 21) (Klamroth-Marganska 2014). Using these data, the mean difference in treatments will have an effect size of 1.9. For a 1-tailed unpaired t-test, **N=5** subjects in each treatment group are needed to detect this difference with power > 0.80. Similarly for the ARAT, we had gains of 5.6 (sd=4.7) after the experimental treatment in our pilot study. A different study (Fleming 2015) reported gains of 1.0 (sd=5.7) after 24 hours of conventional therapy in 17 chronic stroke subjects with similar intake ARAT scores as in our pilot study (ARAT = 26.6 vs. 20.9). Using these data, the mean difference in treatments will have an effect size of 0.84. For a 1-tailed unpaired t-test, **N=19** subjects in each treatment group will detect this difference with power > 0.80.

Therefore with **N=19** subjects in each treatment group, we will detect the anticipated pre-post changes and group differences in the ARAT and Fugl-Meyer. We had a dropout rate of 0.167 in the pilot study. Therefore, we will plan for this and recruit 23 subjects into each treatment group. We have no pilot data on the MAL to perform a power analysis for the outcome.

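### The power above 0.80 that fixes N=19 per group is for one 1-tailed t-test at 0.05, which is not the test the Data analysis section plans; on the plan's own d=0.84, ARAT power is at most 0.71 two-sided and about 0.60 with Bonferroni

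*Combined protocol and SAP*

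**What the plan says.** **Power Analysis.** For Hypotheses I and II the sample sizes are those needed "when using a 1-tailed paired t-test with" alpha .05: N=8 and 18 for Hypothesis I (ARAT, Fugl-Meyer) and N=16 and 6 for Hypothesis II, each for power above 0.90. For Hypothesis III on the Fugl-Meyer: "For a 1-tailed unpaired t-test, N=5 subjects in each treatment group are needed to detect this difference with power > 0.80". For Hypothesis III on the ARAT, "the mean difference in treatments will have an effect size of 0.84", and then: "For a 1-tailed unpaired t-test, N=19 subjects in each treatment group will detect this difference with power > 0.80". The section concludes, without qualification, that 19 per group will detect the anticipated changes and differences. Recruitment of 23 per group follows from that figure.

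**Data analysis.** Paired t-tests are planned for Hypotheses I and II, with no tail stated. For the group comparison: "To test Hypothesis III, the timepoint x group interaction effect will be examined in the mixed model ANOVA". Only if that is significant are gains at the post-treatment and 6-month timepoints compared by unpaired t-tests with Bonferroni corrections, again with no tail stated. The only directional wording is for the z-test on the proportion of subjects gaining 10% or more.

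**Aims / Hypotheses.** Hypothesis III is worded directionally, and Hypotheses I and II refer to p < 0.05 without a tail.

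**Background.** Pilot results are quoted with p-values, for example "gain=5.6±2.1; p=.057" for the ARAT.

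**The concern.** A sample size is informative only for the test it was computed for. Here the calculation assumes a single directional t-test at the full 0.05, whereas the analysis section describes a non-directional F-test followed by corrected t-tests whose direction is left open. Two things are at stake. First, the claim of more than 80% power for the ARAT group difference, which alone determines enrolment, may be materially too high, so a null ARAT result would look more informative than it is. Second, an unstated tail can be settled after the data are seen, and in a small trial that choice can move a result across 0.05.

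**Working it through.** **Inputs.** From Power Analysis: d=0.84 (Hypothesis III ARAT), d=1.9 (Hypothesis III Fugl-Meyer), d_z=1.2 and 0.74 (Hypothesis I ARAT, Fugl-Meyer), d_z=0.77 and 1.41 (Hypothesis II ARAT, Fugl-Meyer), and 19 per group. Alpha .05 is stated for Hypotheses I and II. It is not restated for Hypothesis III, but N=19 and N=5 reproduce at 1-tailed 0.05. The number of Bonferroni comparisons is not given; I assume two per outcome (post-treatment and 6 months).

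**Formulas.** Unpaired: noncentrality d·√(n/2), df 2n−2. Paired: noncentrality d_z·√n, df n−1. Power is the noncentral-t probability beyond the critical value.

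**1. The plan's own figure.** d=0.84, n=19: noncentrality 0.84·√9.5 = 2.589, df 36. The 1-tailed 0.05 critical value is 1.688 and power is 0.815; n=18 gives 0.795. So N=19 is correct for the test named. The other five also reproduce 1-tailed: 0.919 (N=8), 0.914 (N=18), 0.902 (N=16), 0.903 (N=6) and 0.863 (N=5 per group).

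**2. Hypothesis III ARAT, same d and n, other readings of the test.**

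| Test | Critical t | Power |
|---|---|---|
| 1-tailed, 0.05 (as sized) | 1.688 | 0.815 |
| 2-sided, 0.05 | 2.028 | 0.712 |
| 1-tailed, 0.025 (Bonferroni, two timepoints) | 2.028 | 0.712 |
| 2-sided, 0.025 (Bonferroni, two timepoints) | 2.339 | 0.601 |

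The d that gives about 0.80 power in a single test is 0.82 for 1-tailed 0.05 and 0.93 for 2-sided 0.05. If all 23 recruits per group completed, 2-sided power at 0.05 would be 0.796.

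**3. The other five comparisons at 2-sided 0.05 with 19 subjects (19 per group for Hypothesis III).** Hypothesis I Fugl-Meyer: noncentrality 0.74·√19 = 3.226, critical t 2.101, power 0.862. Hypothesis II ARAT: 0.77·√19 = 3.356, power 0.887. Both are below the stated 0.90. Hypothesis I ARAT, Hypothesis II Fugl-Meyer and Hypothesis III Fugl-Meyer are all above 0.99.

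**4. The F-test gate.** Assume compound symmetry and a gain SD common to all timepoints, and express the group differences δ_j in gain-SD units. The interaction F then has 3 and 108 df, critical value 2.689 and noncentrality n·Σ(δ_j − mean δ)², which does not depend on the within-subject correlation. For assumed patterns at pre, 12 h, 24 h and 6 months:

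| δ pattern | Noncentrality | Chance of passing |
|---|---|---|
| 0, 0.42, 0.84, 0.42 | 19·0.3528 = 6.70 | 0.55 |
| 0, 0.42, 0.84, 0.84 | 19·0.4851 = 9.22 | 0.71 |
| 0, 0.84, 0.84, 0.84 | 19·0.5292 = 10.05 | 0.75 |
| 0, 0, 0.84, 0.84 | 19·0.7056 = 13.41 | 0.87 |

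A positive result needs both the gate and the t-test, so overall power cannot exceed the smaller of the two.

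**5. Pilot p-values.** Read the ± values in Background as standard errors and take the SDs from Power Analysis: (4.9/2.2)² = 4.96 and (4.7/2.1)² = 5.01, so n=5. ARAT: t = 5.6/2.1 = 2.67 on 4 df, 2-tailed p=0.056, 1-tailed 0.028 (stated .057). Fugl-Meyer: t = 7/2.2 = 3.18, 2-tailed p=0.0335, 1-tailed 0.017 (stated 0.034). Both match 2-tailed tests only.

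**The case against.** The best defence is that the hypotheses are directional, the Power Analysis openly declares 1-tailed tests of the kinds the analysis section plans, and no passage says 2-sided. On that view the silence in Data analysis is under-specification, not contradiction, and 0.71 is the power of a test the plan never adopted. Much of this stands: the 2-sided figures are conditional. It does not rescue the stated power, however. Read as 1-tailed, the plan still applies Bonferroni, and for two timepoints that gives the same 0.71, still behind an F-test the sample size ignores.

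A reader might also infer stronger points that the documents do not support:

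- **That the document sets a 2-sided standard.** It does not. Two of the six pilot p-values can be checked, on an inferred n, and they fit 2-sided reporting. That supports the convention but neither proves it nor fixes the tail for this trial.
- **That 1-tailed testing doubles false claims of robot superiority from 2.5% to 5%.** That describes a single ungated, uncorrected test. I simulated the null for one outcome (400,000 trials, 19 per group, four timepoints, compound symmetry, F gate at 0.05, Bonferroni over two timepoints). A false robot-better result occurred in about 1.5% of trials with 1-tailed follow-ups and 1.2% with 2-sided ones.
- **That a worse robot arm could not be seen.** The F-test can reject in that direction, and gains are calculated by group.
- **That all six calculations fail.** Two-sided power at N=8, 6 or 5 is irrelevant to a trial with 19 per group.

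**Conclusion.** The point holds in limited form. The stated power above 0.80 at 19 per group is arithmetically right for one 1-tailed t-test at 0.05, but that is not the analysis described. For the deciding ARAT comparison, power is at most 0.71 as a single 2-sided test and about 0.60 with 2-sided Bonferroni over two timepoints, with the F gate a further limit. Two pre-post comparisons fall slightly short of their stated 0.90 at 2-sided 0.05 (0.86 and 0.89), and three are unaffected in practice.

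These figures rest on the plan's own effect sizes, 19 completers per group, a Bonferroni count of two that the plan does not state, and, for the gate, assumed gain patterns. Taking d=0.84 as given does not endorse it: Background attaches the 5.6-point ARAT gain to the robot-only period, while Power Analysis attributes it to the full experimental treatment.

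**What to change.** In Data analysis, state that the t-tests of Hypotheses I to III are 2-sided at 0.05, which is consistent with the non-directional F-test, and state how many comparisons the Bonferroni correction covers.

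Restate the Power Analysis on that basis at 19 per group. Hypothesis III ARAT has at most 0.71 for d=0.84 as a single test and about 0.60 with Bonferroni for two timepoints, further limited by the interaction gate. Before any Bonferroni correction, Hypothesis I Fugl-Meyer has 0.86, Hypothesis II ARAT 0.89, and the other three comparisons above 0.99. The 0.71 should be labelled as the single-test figure, not as the power of the whole procedure. Remove the unqualified statement that the anticipated changes and differences will be detected.

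The cost is wording in two sections, with no extra subjects and no new procedures. The downside is a less favourable stated power.

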## **6. Data Monitoring, Information Security and Safety**

The PI and co-investigator ([name]) will oversee safety for the study; and an independent study monitor will be identified if the DCVAMC requires one. Frequent rest breaks

will be offered during the laboratory-based testing. Should complications occur, [name] will oversee management until care can be transferred to the participant's caregivers. All data collected will remain confidential. Data will be coded by subject number according to an established laboratory convention and reference made to individual subjects only in this manner. All raw data in the form of hard copy materials and computer files remain property of the laboratory under the direction of the Principal Investigator. The study records will remain the property of the Principal Investigator's laboratory and be destroyed according to the VA Records Control Schedule (RCS). All identifying personal information will be removed from the data. The master list of subject codes and the corresponding subject names will be kept in a locked filing cabinet and not leave the DC VA Medical Center. All data will be stored in the Clinical Research Center, Human Performance Research Unit, room #1043. All electronic data will be stored on VA networked drives. If data is stored on PC hard drives, the PC will be encrypted. No mobile devices will be used to store data and data will not be removed from the VA-protected environment. Study personnel who leave the study will not longer have access to the data. Standard procedures are in place for reporting incidents, i.e. theft or loss of data or storage media, unauthorized access of sensitive data or storage devices or non-compliance with security controls.

## **9. Project Schedule**

Testing will begin approximately on 6/16 and continue for four years.

## **10. Problems / Weaknesses**

Identifying and recruiting the participation of appropriate subjects will be a challenge for this study. Substantial plans have been established to address subject accrual and have been budgeted accordingly. Recruitment efforts will begin at the DCVAMC and expand to local facilities as needed.

## **11. Monitoring and Reporting Adverse Events**

The anticipated adverse events are all mild. These adverse events will be retained in a study binder for review by the study team. Unanticipated adverse events of a serious nature will reported to the IRB within 2 days.

## **12. Risk / Benefit Assessment**

Potential risks posed to those who decide to participate in this study include the rare possibility of muscle and/or joint soreness related to over-exertion; similar to the soreness felt after using exercise equipment. Additionally, the possibility exists that participants may experience skin irritation from the use of tape on the skin during the motion capture, or from pressure points from contact with the robot. Subjects will be encouraged to discuss such risks with the investigator, the subjects' primary care physicians, and/or family and friends before agreeing to participate in study.

According to FDA guidelines, the robot and hand exoskeleton are classified as a non-significant risk investigational device because:

- 1) The device is not an implant.
- 2) The device is not used in supporting or sustaining life.
- 3) The device is not of substantial importance in diagnosing, curing, mitigating or treating disease, or otherwise prevents impairment of human health.
- 4) The device does not present a potential for serious risk to the health, safety, or welfare of the subject.

There may be direct benefits related to subject participation in this research study; however, this is not guaranteed to be the case for all subjects who participate.

## **13. Study Population**

No gender and/or ethnicity will be excluded from participating in the study. The study will attempt to maintain a balanced cohort based on both gender and ethnicity.

## **14. Recruitment Plan**

Subjects will be recruited from the outpatient clinics at the Washington DC VAMC. The DC VAMC annually has over 100 admissions for stroke. [name], has WOC status at the DC VAMC and will confirm that patients meet study criteria. Additionally, veterans will be recruited from nearby MedStar National Rehabilitation Hospital (NRH), Washington Hospital Center (WHC), and Medstar Health outpatient clinics.

## **15. Vertebrate Animals**

N/A

## **16. Consultants**

N/A

## **17. Curriculum Vitae**

Attached

## **18. Compliance**

The trial will be conducted in compliance with the protocol, HHS, FDA, ICH, VA and all applicable institutional state and local requirements.

